7.7 Guidelines for Determining Causality of an Adverse Event

The investigator will use the following question when assessing causality of an AE to IP: Is there a reasonable possibility that the IP caused the event?

An affirmative answer designates the event as a suspected adverse reaction.

7.8 Adverse Event Collection Procedures

Any new event or experience that was not present at Screening, or worsening of an event present at Screening, is considered to be an AE. Unchanged, chronic conditions are not AEs and should not be recorded on the AE page of the CRF. Adverse events will be evaluated from the onset of the event until the time the event is resolved or medically stable, or until 30 days after the subject completes study treatment, whichever comes first. Adverse events ongoing at the time that study treatment is discontinued may not be determined to be medically stable until 30 days after the Exit or Early Discontinuation Visit has been conducted, in which case additional visits after the Exit or Early Discontinuation Visit will be required. Investigators should also report AEs discovered after cessation of dosing and prior to the Early Discontinuation Visit.

AEs may be discovered through any of these methods:

- Observing the subject

- Questioning the subject, which should be done in an objective manner
- Receiving an unsolicited complaint from the subject
- Review of medical records/source documents
- Review of home dosing symptom diary (provided to record symptoms between visits)

7.8.1 AE Recording Procedures

AEs are recorded within the electronic data capture (EDC) system as detailed in the CRF completion guidelines.

7.8.2 SAE Recording and Reporting Procedures

All SAEs will be reported to the sponsor from the time of signing of the ICF through the Early Discontinuation/Exit Visit (at least 14 days after the last AR101 dose). If the investigator becomes aware of a SAE in a subject treated by him or her with a suspected causal relationship to the IP that occurs after the end of the study, the investigator shall without undue delay, report it to the sponsor.

SAEs will be recorded on the AE CRF. All centers are obligated to report SAEs within 24 hours of their occurrence and/or the site's knowledge of the event to the sponsor. The following attributes will be assigned:

- Description
- Date of onset and resolution (if known when reported)
- Severity
- Assessment of relatedness to test article
- Action taken

The site investigator will apply his or her clinical judgment to determine whether an AE is of sufficient severity to require that the subject be removed from treatment. If necessary, an investigator will suspend any trial procedures and institute the necessary medical therapy to protect a subject from any immediate danger.

Subsequent review by regulatory health authority(ies), the DSMC, institutional review board (IRB)/ EC, or the sponsor(s) may suspend further trial treatment or procedures at a site. The study sponsor(s) and the regulatory health authorities retain the authority to suspend additional enrollment and treatments for the entire study as applicable.

1. Notify the site's investigator.
2. Complete and transmit an AE form through the EDC system. Information regarding an SAE report must be recorded in the subject's medical chart.
3. Complete and submit an SAE Form in accordance with the SAE completion guidelines.

4. SAE follow-up reports should include, as applicable, hospital admittance notes, hospital discharge summary, clinical notes, resolution date, treatment, and any other pertinent information regarding the event. Reporting should not be delayed in order to provide these documents.
5. In the event of a death, the SAE form must be completed and transmitted along with other supporting data (death certificate, medical notes, etc).

7.9 Serious Adverse Event Notification

7.9.1 Notifying the Sponsor

Study investigators will provide the drug safety vendor with data of all SAEs as defined per the protocol on an ongoing basis.

The drug safety vendor is responsible for notifying the sponsor and will do so simultaneously with the reporting to the clinical database. As noted above, this should be within 24 hours of site awareness of the event.

7.9.2 Expedited SAE Reporting to Regulatory Health Authorities

The medical monitor will review each SAE report and will determine whether the SAE must be reported to regulatory health authorities on an expedited basis. The final decision for disposition regarding expedited reporting to the regulatory health authorities rests with the medical monitor.

The sponsor will expedite the reporting to all concerned investigator(s), the EC, where required, and to the regulatory health authorities, including (when applicable) via EudraVigilance Clinical Trial Module (EVCTM) in accordance with CT-3, Article 7.4, reports of all adverse drug reactions (ADRs) that are both serious and unexpected in accordance with ICH E6 5.16.2 and 5.17.1.

Specifically, the sponsor shall ensure that all relevant information about suspected serious unexpected adverse reactions that are fatal or life-threatening are recorded and reported as soon as possible to the competent authorities in all the Member States concerned, and to the EC no later than 7 days after knowledge by the sponsor of such a case, and that relevant follow-up information is subsequently communicated within an additional 8 days. All other suspected serious unexpected adverse reactions shall be reported to the appropriate regulatory health authorities and to appropriate EC as soon as possible and within a maximum of 15 days of first knowledge by the sponsor. In addition, such expedited reports will comply with the applicable regulatory requirement(s) and with the ICH E2A Guideline for Clinical Safety Data Management: Definitions and Standards for Expedited Reporting and ICH E6 5. The sponsor will provide the DSMC and the drug safety vendor with copies of any expedited SAE reports submitted to regulatory health authorities.

The drug safety vendor will provide these expedited reports to the individual site investigators. Events that are serious, related to therapy, and unexpected will be reported to regulatory health authorities within 15 days or for deaths and life-threatening events within 7 days (as per applicable regulatory reporting requirements).

Finally, the sponsor will submit to the regulatory authorities all safety updates and periodic reports, as required by applicable regulatory requirements including ICH E6 5.17.3 and ICH E2F.

7.9.3 Notifying the Data Safety Monitoring Committee

The drug safety vendor will provide the DSMC with listings of all SAEs on an ongoing basis. Furthermore, the DSMC will be informed of expedited SAE reports. Periodic reports from the DSMC as to the overall safety of the ongoing study, and recommendations regarding continuation will be sent to the investigators for forwarding to their ECs if requested.

Sites are instructed to report episodes of anaphylaxis within 24 hours of their occurrence and/or the sites being notified of the event to the drug safety vendor. Information regarding these events will be sent to the DSMC if the event is associated with any of the following:

- Fatal ADR;
- An ER visit;
- Hospitalization;
- Three or more doses of epinephrine being given as treatment for the same episode;
- Assessment of the anaphylaxis as severe, as defined in [Appendix 3](#).

An initial Adverse Event of Interest form containing the information known to the site at the time will be transmitted to the drug safety vendor. The drug safety vendor will then relay to the sponsor and DSMC the individual anaphylaxis reports as they are obtained. The site will supplement the initial Adverse Event of Interest form with additional information pertaining to an event as it becomes available and will forward the information to the drug safety vendor.

7.9.4 Notifying the Institutional Review Board and Ethics Committee

The investigator will ensure the timely dissemination of all AE information, including expedited reports and DSMC safety reviews, to the EC in accordance with applicable local regulations and guidelines.

Once a year throughout the clinical trial, the sponsor shall provide the Member States in whose territory the clinical trial is being conducted and the EC with a listing of all suspected serious adverse reactions that have occurred over this period and a report of the safety of subjects.

7.10 Other Safety Assessments and Precautions

7.10.1 Physical Examination and Vital Signs

Physical examinations will be conducted at visits indicated in [Appendix 1](#) Schedule of Events. Height and weight will also be recorded at specified visits. Vital signs will be measured, including BP, pulse rate, and body temperature. Except where a full, age appropriate, physical examination is specifically indicated, a symptom-directed physical exam may be performed.

7.10.2 Prior and Concomitant Medications

Prior and concomitant medications will be duly documented in the CRF.

7.10.3 Pregnancy Testing and Contraception

7.10.3.1 Pregnancy Testing

All female subjects of childbearing potential will undergo a serum pregnancy test at Screening and then urine pregnancy test at subsequent visits.

Females of childbearing potential are defined as all women physiologically capable of becoming pregnant, including women whose career, lifestyle, or sexual orientation precludes intercourse with a male partner and women whose partners have been sterilized by vasectomy or other means, UNLESS they meet the following criteria: at least 12 months of natural (spontaneous) amenorrhea or 6 months of spontaneous amenorrhea with serum follicle stimulating hormone (FSH) levels > 40 IU/L or at least 6 weeks post-surgical bilateral oophorectomy with or without hysterectomy or hysterectomy, OR are using one of the methods of highly effective contraception listed in Section [7.10.3.2](#).

Although pregnancy itself is not considered an AE or an SAE, if a subject becomes pregnant during the course of the study the pregnancy must be reported to the sponsor and the subject should be followed to term or until termination.

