4. SELECTION AND WITHDRAWAL OF SUBJECTS

4.1 Inclusion Criteria

Subjects who meet all of the following criteria are eligible for enrollment as study subjects:

1. Age 4 through 17 years (inclusive)
2. Clinical history of allergy to peanuts or peanut-containing foods

3. Serum IgE to peanut of ≥ 0.35 kUA/L (as determined by UniCAP™ within the past 12 months) and/or a peanut SPT wheal diameter ≥ 3 mm compared to control
4. Experience DLS at or before the 300 mg (444 mg cumulative) challenge dose of peanut protein (measured as 600 mg of peanut flour) on Screening DBPCFC conducted in accordance with PRACTALL guidelines
5. Written informed consent from subjects or parent/guardian for all subjects (or both parents when required by local authorities)
6. Written assent from minor subjects as appropriate (in accordance with local regulatory requirements)
7. Use of effective birth control by female subjects of childbearing potential ([Section 7.10.3.2](#))

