- Serum pregnancy test for females of childbearing potential (pregnancy test result must be available prior to the DBPCFC)
- Blood draw (same venipuncture for all samples), at any time during Screening prior to the DBPCFC, to collect samples for:
 - Peanut- and peanut component-specific IgE, total IgE, and peanut-specific IgG4 assays
 - Complete blood cell count (CBC)
 - Optional blood sample for immune cell characterization assays

The amount of blood to be taken in total for all tests (required immunoglobulin and CBC and optional immune cell characterization assays) will be included in the manual of procedures and not exceed a total volume of 2.5 mL/kg, to a maximum total of 70 mL on any study day. Blood draw should be collected in compliance with local laboratory guidelines and testing regulations. Multiple attempts to obtain blood, and repeat samples can be collected where necessary for damaged samples or safety reasons.

- SPT to peanut extract
- Confirmation subject or subject's parent or guardian has an unexpired epinephrine auto-injector prior to leaving the clinic following Day 1 of the DBPCFC

- DBPCFC conducted in accordance with PRACTALL guidelines, with assessments made by a Blinded Evaluating Physician (Blinded Assessor), as described in [Section 6.6](#).
- Monitoring for AEs, including allergic symptoms ([Section 6.7](#)) commences from the time the consent/assent form is signed
- Subjects will be instructed to continue to follow a peanut-avoidant diet for the duration of the study.
- Subjects and parents or guardians will additionally receive teaching about food/peanut allergy according to the investigational site's established standards. This is to include at a minimum the following topics (some or all of which may be addressed in a comprehensive anaphylaxis action plan):
 - Recognition of an allergic reaction and of the symptoms of anaphylaxis
 - When and how to administer epinephrine via auto-injector
 - Requirement to go to nearest emergency facility following use of epinephrine auto-injector
 - Ways to minimize the risk of accidental exposure to peanut in, and outside of, the home (may be supplemented by referral to recognized food allergy organizations for access to additional learning materials)

The laboratory values and clinical findings, including those from the Screening DBPCFC, will serve as the baseline measures for comparison to subsequent measures obtained during the course of the study.

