The 80 mg Up-dosing Visit is the approximate midpoint of the Up-dosing Period. At the 80 mg Up-dosing Visit the following procedures are to be performed in addition to those performed at the other Up-dosing Visits:

- Complete physical examination, including height and weight
- In subjects with asthma: evaluation of asthma severity using the 2007 NHLBI Criteria ([Appendix 2](#)) and the Asthma Control Test questionnaire
- Urine pregnancy test for females of childbearing potential

- Review home dosing instructions
- Review with subjects and parents or guardians teaching about food/peanut allergy according to the investigational site's established standards. This is to include at a minimum the following topics (some or all of which may be addressed in a comprehensive anaphylaxis action plan):
 - Recognition of an allergic reaction and of the symptoms of anaphylaxis
 - When and how to administer epinephrine via auto-injector
 - Requirement to go to nearest emergency facility following use of epinephrine auto-injector
 - Ways to minimize the risk of accidental exposure to peanut in, and outside of, the home (may be supplemented by referral to recognized food allergy organizations for access to additional learning materials)

6.3.3.3 300 mg Up-dosing Visit

At this visit the following procedures are to be performed in addition to those performed at the Up-dosing Visits:

- Complete physical examination, including height and weight
- In subjects with asthma: evaluation of asthma severity using the 2007 NHLBI Criteria ([Appendix 2](#)) and the Asthma Control Test questionnaire
- Urine pregnancy test for females of childbearing potential
- Blood draw (same venipuncture for all samples) to collect samples for:
 - Peanut- and peanut component-specific IgE, total IgE, and peanut-specific IgG4 assays
 - CBC
 - Optional blood sample for immune cell characterization assays

The amount of blood to be taken in total for all tests (required immunoglobulin and CBC and optional immune cell characterization assays) will be included in the manual of procedures and will not exceed a total volume of 2.5 mL/kg, to a maximum total of 70 mL on any study day. Blood draw should be collected in compliance with local laboratory guidelines and testing regulations. Multiple attempts to obtain blood, and repeat samples can be collected where necessary for damaged samples or safety reasons.

- SPT to peanut extract
- Review home dosing instructions

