7.10.3.2 Contraception

Subjects undergoing OIT are at increased risk for experiencing allergic reactions and may be at increased risk for experiencing anaphylaxis. Anaphylaxis can cause a dangerous drop in BP; and if this were to occur during pregnancy, it could result in compromised placental perfusion and significant risk to the fetus.

Pregnancy is a time when the mother's immune system undergoes complex and incompletely understood changes that are believed to reduce the risk of a maternal immune reaction directed against the fetus. It is also a time when the fetus's immune system is developing. OIT, at its core, entails repeated stimulation of the immune system to affect changes in its makeup and function. What effects OIT-induced changes in the immune system might have on the course of pregnancy or fetal development are currently unknown. Accordingly, female subjects of childbearing potential are required to practice approved and effective birth control for the duration of the current study.

Study personnel are requested to address questions of sexual history and counselling in relation to contraception using sensitivity and a patient-centered approach and, if possible, to hold discussions regarding sexual history and contraception with adolescent female subjects in a private setting.

Female subjects are to use a highly effective single method of birth control, defined as one that results in a low failure rate (ie, less than 1 percent per year) when used consistently and correctly. Acceptable methods of birth control are the following:

- Combined (oestrogen and progestogen containing) hormonal contraception associated with inhibition of ovulation (oral, intravaginal or transdermal)
- Progestogen-only hormonal contraception associated with inhibition of ovulation (oral, injectable or implantable)
- Intrauterine device (IUD)
- Intrauterine hormone-releasing system (IUS)
- Bilateral tubal occlusion
- Sexual abstinence

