- p) Palatability questions to be answered before the Exit DBPCFC.
- q) For females of childbearing potential only. To be performed and results obtained prior to DBPCFC, where applicable.
- r) Blood draw for IgE and IgG4 is to be drawn prior to DBPCFC.
- s) Separate informed consent required. No more than 2.5 mL/kg may be drawn, up to a maximum of 70 mL on any one study day. Multiple attempts to obtain blood, and repeat samples can be collected where necessary for damaged samples or safety reasons.
- t) It must be verified that the subject has an epinephrine auto-injector prior to the subject leaving the clinic on day 1 of the Screening DBPCFC.
- u) At the end of the Screening period, eligible subjects who satisfy all other Screening requirements, will undergo a DBPCFC a maximum challenge dose of 300 mg (444 mg cumulative).
- v) Subjects who up-dose to 300 mg and maintain this dose for approximately 12 weeks without symptomatic therapy for at least the last 4 weeks will undergo the Exit DBPCFC at the end of Maintenance Period to a maximum challenge dose of 1000 mg (2043 mg cumulative).
- w) AEs and allergic symptoms will be collected from the point of signing the ICF until 30 days after the subject completes study treatment. Each event should be evaluated from the point of onset until the event is resolved or medically stable, or until 30 days after the subject completes study treatment, whichever comes first. Subjects with ongoing AEs at early discontinuation or study exit will have safety follow-up for at least 30 days or until the AEs resolve or stabilize, whichever is last ([Section 4.3.2](#)). Subjects who have gastrointestinal AEs with prolonged disruption of dosing or who discontinue treatment due to gastrointestinal AEs will have safety follow-up for 6 months or until the chronic/recurrent gastrointestinal AE resolve or stabilize, whichever is last. These subjects will complete the PEESS v2.0 questionnaire while symptomatic, at the time of treatment discontinuation, and monthly for 6 months during safety follow-up ([Section 7.3.3.2](#)). Subjects may complete the PEESS v2.0 at home and send it to the clinic, or at the clinic if they have monthly clinic visits. Subjects who discontinue treatment due to gastrointestinal AEs will be asked to return to the clinic for evaluation monthly for at least 6 months (if asymptomatic, telephone follow-up may be appropriate per investigator discretion).

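### The definition of childbearing potential drops anyone using a listed contraceptive method, abstinence included, so a subject who meets the contraception requirement is exempt from every scheduled pregnancy test while she uses it

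*Protocol*

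**What the plan says.** Section 7.10.3.1 orders a serum pregnancy test at Screening and urine tests later, for females of childbearing potential. It defines them broadly as those physiologically able to become pregnant, "including women whose career, lifestyle, or sexual orientation precludes intercourse with a male partner". It then lists exceptions. Most concern loss of reproductive capacity: prolonged amenorrhea, oophorectomy, hysterectomy. The last is different in kind. It removes subjects who "OR are using one of the methods of highly effective contraception listed in Section" 7.10.3.2.

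The list in Section 7.10.3.2 covers hormonal methods, intrauterine devices and systems, and tubal occlusion, and it ends with "Sexual abstinence". The same section says that "female subjects of childbearing potential are required to practice approved and effective birth control for the duration of the current study". Inclusion criterion 7 in Section 4.1 makes this an entry condition: "Use of effective birth control by female subjects of childbearing potential", with a reference to 7.10.3.2.

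The tests themselves are ordered as follows:

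- Section 6.2: "Serum pregnancy test for females of childbearing potential (pregnancy test result must be available prior to the DBPCFC".
- Sections 6.3.3.2 (80 mg visit), 6.3.3.3 (300 mg visit), 6.4 (Early Discontinuation) and 6.5 (Exit): "Urine pregnancy test for females of childbearing potential".
- Appendix 1, note q, attached to both the serum and the urine rows: "For females of childbearing potential only. To be performed and results obtained prior to DBPCFC, where applicable".

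**The concern.** The group that must use contraception ceases to be that group once it does so, and the pregnancy tests are tied to membership of the group. A subject using a listed method is therefore not required to have any test while she uses it. Only a candidate not yet on a method, or a subject who lapses, would have to be tested.

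The protocol does not state the purpose of the tests. The natural reading is that they catch method failure and misreported use or abstinence, and those are the cases that the clause exempts.

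The stake is subject safety. Pregnancy is exclusion criterion 16 and the third termination reason in Section 4.3.1. Section 7.10.3.2 describes anaphylaxis in pregnancy as a significant risk to the fetus and calls the effect of oral immunotherapy on pregnancy unknown. A pregnancy missed at Screening would be carried into a peanut challenge that continues until dose-limiting symptoms occur or the top dose is reached, and then into up-dosing.

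**Working it through.** No figure in the protocol needs reproducing. The check is a reading of the definition against each place that uses it, followed by a count of tests.

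**Step 1: is contraceptive use really an exception?** In Section 7.10.3.1 the clause follows the word that opens the exceptions and is joined to the others by a capitalised OR. It is therefore one more way to fall outside the definition. It is in the present tense, so the exemption lasts as long as the method is in use.

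**Step 2: does any test order escape the definition?**

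| Test | Place | Limited to females of childbearing potential? |
|---|---|---|
| Serum, Screening | 6.2; 7.10.3.1; Appendix 1 note q | Yes |
| Urine, 80 mg visit | 6.3.3.2; note q | Yes |
| Urine, 300 mg visit | 6.3.3.3; note q | Yes |
| Urine, Early Discontinuation | 6.4; note q | Yes |
| Urine, Exit | 6.5; note q | Yes |

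Appendix 1 also marks a urine test at Unscheduled Visits, under the same note q. No other text orders testing of contraceptive users.

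**Step 3: count the tests required under the literal definition.**

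- Completer: 1 serum (Screening) + 2 urine (80 mg, 300 mg) + 1 urine (Exit) = 4 scheduled.
  - Listed method from Screening on: 0 of 4 required.
  - Method started after the Screening test and continued: 1 of 4 required.
  - Lapse during the study: only the tests that fall while she is off a method are added.
- Early discontinuer: 1 (Screening) + 1 (Early Discontinuation) = 2 scheduled, rising to 3 if the 80 mg visit was reached and to 4 if the 300 mg visit was also reached.
  - Listed method from Screening on: 0 of these 2 to 4 required.

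**Step 4: set the definition against the rest of the protocol.**

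- Criterion 7 and Section 7.10.3.2 address females of childbearing potential as people who use contraception throughout the study. Under Section 7.10.3.1 nobody using a listed method belongs to that group. Both cannot be right.
- The main clause of the definition keeps in those whose lifestyle precludes intercourse. The last exception takes out those who name abstinence as their method. The overlap is partial, but it is a conflict for those subjects.

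**Step 5: do other safeguards fill the gap?** Contraception is reviewed at Up-dosing and Maintenance visits (Sections 6.3.3.1 and 6.3.4), and a diagnosed pregnancy must be reported within 24 hours (Section 7.3.1). Neither detects a pregnancy that nobody has recognised.

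**The case against.** The strongest reply is that the protocol, read as a whole, plainly intends contraceptive users to be tested. If every user left the group, the urine tests after Screening would apply to almost nobody, yet they are scheduled at four named visits. A site working from Appendix 1 would probably test every post-menarchal girl. This stands as a prediction of practice, and it makes 0 of 4 a worst-case reading of the text and not an expected outcome. It does not rescue the text: a site that skips the tests would be following the definition as written.

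Second, Section 7.10.3.2 also says, without the qualifier, that female subjects are to use a highly effective method. That preserves the duty to use contraception, so the damage is confined to testing. No comparable unqualified sentence preserves the tests.

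Third, an exception that narrows a general rule is not in itself a contradiction. Subjects with a vasectomised partner stay in, because vasectomy is not a listed method, and sexual orientation that precludes intercourse with a male partner is not the same as abstinence. This is fair. The conflict inside the sentence holds only for those who name abstinence as their method, and the main point does not depend on it.

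Finally, the listed methods are described as failing in under 1 percent per year when used consistently and correctly, exclusion and termination for pregnancy apply to every subject, and the number affected is unknown. These limit the residual risk. They do not replace a test where use is inconsistent or misreported.

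**Conclusion.** The concern holds. As written, the definition exempts a subject who complies with the contraception requirement from all scheduled pregnancy tests for as long as she uses a listed method: 0 of 4 for a completer and 0 of 2 to 4 for an early discontinuer, if she uses one from Screening on. This rests on a literal reading of Section 7.10.3.1 and on the absence of any other instruction to test contraceptive users.

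The number of subjects concerned cannot be given. The trial randomizes about 160 subjects aged 4 to 17, and the protocol does not state how many are expected to be post-menarchal. No efficacy endpoint, analysis population or error rate is touched. It is a safety rule that is wrong as written and should be corrected.

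**What to change.** In Section 7.10.3.1, delete from the list of exceptions the clause that begins "OR are using one of the methods of highly effective contraception listed in Section", together with the reference to 7.10.3.2 that completes it. The sentence then ends with the amenorrhea and surgical criteria, and contraceptive users remain females of childbearing potential.

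Inclusion criterion 7, Section 7.10.3.2 and Appendix 1 with note q can stay as they are, because they already assume that meaning. The cost is one deleted clause, with no visits or tests beyond those already in Appendix 1.
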